Stability of the Medial Pivot Total Knee Prosthesis

PRINCIPAL INVESTIGATOR:

[name]
Department of Orthopaedic Surgery
[name]
[name]

SUB-INVESTIGATORS:

[name]
University of Chicago

[name]
Northwestern University

[name]
Northwestern University

[name]
Northwestern University

[name]
Northwestern University

PARTICIPATING SITES:

Northwestern Memorial Hospital

Synopsis

Title	Stability of the Medial Pivot Total Knee Prosthesis
Short Title	Medial Pivot Knee Stability
Protocol Date	04/08/2016
Study Duration	2 years
Study Center(s)	Northwestern Memorial Hospital, Northwestern Memorial Faculty Foundation, Northwestern University
Objectives	To compare objective and subjective measures of knee stability following total knee arthroplasty with a medial pivot design vs. a posterior stabilized design
Number of Subjects	100 (50 in each group)
Diagnosis and Main Inclusion Criteria	Patients requiring total knee arthroplasty that present to Northwestern Memorial Hospital or to [name] or [name] clinic

TABLE OF CONTENTS

Synopsis.....
1.0 Introduction.....
2.0 Study Objectives.....

1.0 INTRODUCTION - BACKGROUND AND RATIONALE

Several different prostheses are available for use in total knee arthroplasty (TKA) (1). These designs aim to replicate the normal kinematics of the knee joint while maintaining stability throughout a full range of motion. The posterior cruciate ligament (PCL) contributes to these functions in the native knee, and if preserved it can function similarly in the prosthetic knee (2, 3). Prostheses in which the PCL is sacrificed, and its function not replaced by other means, have poorer outcomes (4). However, various problems with preserving the PCL, including PCL deterioration in arthritic knees (5) and difficulties with proper tensioning (6, 7), have led to the development of alternative ways to emulate normal femoral rollback and sagittal plane stability. These posterior-substituted (PS) designs substitute for the PCL with either a cam and post mechanism or a symmetrical ultra-congruent tibial insert (8, 9).

The cruciate-retaining (CR) and PS designs, together with advances in surgical techniques and component materials, have achieved excellent implant survivorship with rates of > 90% at 20 years (10, 11). Reports of functional outcomes, however, have been variable (12). One potential area for improvement in TKA is optimization of implant design to better approximate native knee kinematics. In the normal knee, the medial condyle remains stable in the sagittal plane, functioning like a ball-and-socket, whereas the lateral condyle translates anterior to posterior during flexion (13-15). The designs of the CR and PS knees do not allow for this medial-centered rotation. Analysis has revealed paradoxical anterior sliding of the femur during flexion, abnormal axial rotation, and condylar lift-off (16, 17). Edge loading and increased sagittal plane motion may predispose to accelerated polyethylene wear (18, 19). The posterior stabilized design uses a cam-and-post mechanism in which one piece of the prosthesis has a plastic post that fits into a slot in the other piece of the prosthesis.

A newer design that attempts to address these issues is the medial pivot knee (MP). This design is characterized by an asymmetrical tibial insert in which the medial compartment is ultra-congruent, providing antero-posterior stability and the lateral compartment allows for rollback around a medial axis of rotation i.e uses a ball-and-socket mechanism. (20) This design more accurately recreates normal knee kinematics, reduces anteroposterior instability, and avoids condylar lift-off (21-24). Early studies indicate improved polyethylene wear characteristics (25). Midterm studies report excellent implant survivorship and clinical outcomes (26, 27).

Several randomized trials have compared the MP knee favorably with other designs. Patients with bilateral TKAs with a different prosthesis on each side preferred their medial pivot knee to a PS, CR, or mobile-bearing (MB) design (28). A trial comparing the MP and PS designs found greater range of motion (ROM) and better patient-reported outcomes in the MP group at 2 years (29). There also exists literature reporting poorer outcomes with the MP design. A trial involving 96 patients who had received both an MP knee and an MB knee on contralateral sides found lower ROM, higher complication rates, and worse patient reported outcomes in the MP knee (30).

Given the lack of consensus in the literature, further investigation is warranted to determine the impact of the MP design on outcomes following TKA.

2.0 OBJECTIVES

The goals of this study are to compare subjective and objective measures of knee stability following TKA with a medial pivot design compared with a posterior stabilized design.

3.0 SELECTION OF SUBJECTS

3.1 INCLUSION CRITERIA

- Age 18-85, regardless of gender, ethnicity, or pathology
- Must require a total knee arthroplasty

- All subjects must have given signed, informed consent prior to registration in study.

3.2 EXCLUSION CRITERIA

- Minors
- Any patients that are unable to consent
- Patients with active infection or osseous tumor of the operative extremity
- Patients undergoing revision surgery

4.0 SUBJECT REGISTRATION

The subjects will be recruited by the PI, co-investigator, or other authorized study staff at the orthopaedic surgery clinic at [name]. The study will be reviewed with the subjects and they will be consented by the PI, co-investigator, or other authorized study staff.

5.0 STUDY DESIGN & METHODS

50 patients will be recruited over 12-18 months. Half of the patients will receive the Medacta GMK Sphere prosthesis (Ball-and-socket), while the other half will receive the Medacta GMK posterior stabilized prosthesis (Cam-and-post). Patients will be randomized in the operating room through the opening of opaque, study-numbered envelopes prior to skin incision.

Patient-reported outcomes will be administered pre-operatively, immediately post-operatively, 6 weeks post-operatively, 3 months post-operatively, 6 months post-operatively, 12 months post-operatively, and 2 years post-operatively. Patient-reported outcomes will be measured using the Oxford knee score (see appendix 1), Knee Society Score, VR-12 (see appendix 2), the Forgotten Joint Score (FJS) for the knee (see appendix 3), and the Kujala Scoring Questionnaire (see appendix 4) as well as the physical function, pain interference, and pain behavior PROMIS CATs (see appendix 5). These questionnaires will be completed at the routine post-operative clinic visits or over the phone through PROMIS Assessment Center. The Forgotten Joint Score (FJS) will only be administered at the subject's 12 month post-operative time point and the Kujala Scoring Questionnaire will only be administered at the subject's 2 year post-operative time point.

At 3-6 months post-op, the operative knee will be examined by a single Sports Orthopaedics attending surgeon [name], who is an expert in assessing knee stability. The attending will grade the stability of the knee in various degrees of flexion according to section 4 of the International Knee Documentation Committee's Knee Ligament Standard Evaluation Form (see appendix 3). KT1000 arthrometer (MEDmetrics, San Diego, CA) measurements will also be taken by a single provider at the 3-month postoperative visit. The patient will also be graded on the get-up-and-go test at this time.

A prospective chart review will be performed starting at the time of enrollment and ending at the study completion date to obtain and verify the following data from NMH Medical records (PRIMES, Cerner PowerChart) and NMFF Medical Records (EpicCare, IDX/GE Centricity):

- EPIC Number
- MRN
- Medical History
- Medications
- Surgical History
- Date of Surgery
- Time taken to complete surgery
- Type of implant

- Post operative quality of prosthesis position/fixation
- Pre and post-operative lab values (Hg, plts, WBC, ESR, CRP, INR, etc)
- Complications/Reoperations
- Knee pathology: Date of onset, age of onset, any associated injuries, radiographic findings, dates and types of prior therapeutic interventions and their effectiveness.
- Physical exam: Specifically, the following information will be obtained: documentation of nerve function, strength, sensation, vascular status, pre-operative stability.
- Outcome data at final follow-up: Ambulatory aid use, orthosis use, job change as result of knee pathology, whether patient went back to work if applicable.

All data collected from chart review will be coded and noted on the Data Collection Form. All patient collected chart data as well as the PROMIS surveys will be coded. The data points will be identified by a random string of five numbers and letters that will be assigned by the PROMIS online database system.

Potential risks involved in this study include the inconvenience of completing questionnaires and stability testing, pain during stability testing, or a fall during the get up and go test. The patient's level of pain will be assessed on the visual analog scale prior to stability testing, and if the degree of pain is felt to be too great by the subject or examiner, the test will be deferred. Inquiry as to the patient's usual level of function will inform the appropriateness of the get up and go test. If the patient does not normally perform transfers into/out of chairs, then those analyses will be deferred. Any ambulation aids that the patient is accustomed to using will be made available.

One possible risk related to the patient's participation in this study is the loss of privacy. To reduce these risks, all of the information collected will be coded (the patient will be assigned a study number and all data will be linked to that number and not the patient's name) and stored in a password-protected file on a password-protected computer. Some of the questions asked may be upsetting, or the patient may feel uncomfortable answering them. If the patient does not wish to answer a question, they may skip it and go to the next question.

Additionally, both knee prostheses included in this study are in common use by orthopaedic surgeons today. Therefore, there are no additional risks involved in the use of these implants for this study.

The subjects are not likely to have any direct benefit from being in this research study. However, the use of the various assessment tools may provide a more accurate assessment of the subject's postoperative pain, function, and satisfaction, and thus help us to better describe and treat any problems that the subject may have after surgery. Beyond these benefits, the subject may benefit from the knowledge that they are helping to improve our understanding of how best to treat future patients that undergo total knee arthroplasty.

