6.0 STATISTICAL PLAN

This proposed sample size is small enough to feasibly recruit over the given time period, yet large enough to correlate differences between the two groups.

Data Cleaning and Crosschecking:

Data cleaning and crosschecking will be conducted prior to analyses. These procedures will include: 1) Comparing patient counts with accrual records; 2) Grouping data by assessment and ensuring a match with the designated number of assessments; 3) Cross-checking baseline and follow-up assessment dates; 4) Ensuring correct questionnaire count match to electronic data fields; 5) Summarizing missing data and checking for definable patterns.

Statistical Analysis:

This study has the primary objective of comparing outcome measures between the MP and PS knee prostheses. We will calculate descriptive statistics for the patient characteristics and measures obtained from each group (means, SD, range). We will use the Shapiro-Wilk test to identify whether each continuous variable fits a normal distribution. We will then use a two-tailed Student's t test for parametric data or the Mann-Whitney U test for nonparametric data to compare the two cohorts. The Pearson χ^2 or Fischer's exact test will be used for categorical variables where appropriate. The level of significance will be defined at $p < 0.05$.

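### The Synopsis plans 100 subjects (50 per group), Section 5.0 recruits 50 in total (25 per group), and nothing in the protocol settles which is meant

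*Combined protocol and SAP*

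**What the plan says.** The sample size comes up in three places.

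- **Synopsis, Number of Subjects:** "100 (50 in each group". The same table has a "Study Duration" entry of 2 years but attaches no recruitment window to the 100.
- **Section 5.0, Study Design & Methods:** the opening sentences set recruitment and its division between the implants: "50 patients will be recruited over 12-18 months. Half of the patients will receive the Medacta GMK Sphere prosthesis (Ball-and-socket". Everyone else gets the posterior stabilized implant. Allocation is then described: "Patients will be randomized in the operating room through the opening of opaque, study-numbered envelopes prior to skin incision".
- **Section 6.0, Statistical Plan:** the only justification offered is one sentence: "This proposed sample size is small enough to feasibly recruit over the given time period, yet large enough to correlate differences between the two groups". No number, effect size, SD, power or dropout rate accompanies this. The analysis is a two-tailed t test or "the Mann-Whitney U test for nonparametric data", at a significance level of 0.05.

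**The concern.** The Synopsis and Section 5.0 cannot both be right. The figure of 25 per group is not printed, but it follows directly from halving the 50 patients in Section 5.0.

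Section 6.0 does not break the tie. Its statement could refer to either total. The only recruitment period in the protocol is the 12-18 months attached to 50. That hints at 50 without establishing it.

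Three things depend on the answer:

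- **The stopping point.** Closing recruitment at 50 completes the trial under Section 5.0 and leaves it half done under the Synopsis. A choice made between the two after the fact is what a fixed sample size is meant to prevent. The data-cleaning step in Section 6.0 that checks patient counts against accrual records also has no single target behind it.
- **The allocation materials.** The envelopes carry study numbers. At one envelope per patient and an even split, the set to prepare is 50 (25 + 25) or 100 (50 + 50).
- **What the trial can show.** Section 6.0 contains no calculation, so the stated number is the reader's only basis for judging the precision of the comparison and the claim of feasibility.

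**Working it through.** **1. The two figures side by side**

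| Source | Total | Per group |
|---|---|---|
| Synopsis | 2 × 50 = 100 | 50 |
| Section 5.0 | 50 | 50 × 1/2 = 25 |
| Section 6.0 | not stated | not stated |

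The ratio is 100/50 = 2. Neither figure can be re-derived, because the protocol gives no effect size, SD, target power or dropout rate.

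**2. Attempts to reconcile them**

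- *Section 5.0 means 50 per group.* This does not fit, because the sentence after the 50 splits those same patients in half.
- *One figure is before dropout and the other after.* Setting 50/(1 − d) = 100 gives d = 0.50. No dropout rate is stated, and Section 5.0 counts patients recruited, not completers.
- *Stages or a per-site split.* The protocol describes neither.

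**3. Effect on what can be detected (illustrative)**

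The plan supplies a two-sided 0.05 level, the t test and equal groups. The assumptions are a continuous outcome, complete follow-up, 80% power for the detectable difference, and the effect sizes shown below.

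The normal approximation to the detectable difference is (1.96 + 0.842) × √(2/n):

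- n = 50: 2.802 × √0.04 = 0.56 SD
- n = 25: 2.802 × √0.08 = 0.79 SD

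The exact values use the noncentral t distribution with noncentrality d × √(n/2) and 2n − 2 degrees of freedom:

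| Quantity (t test) | 50 per group | 25 per group |
|---|---|---|
| Detectable at 80% power | 0.566 SD | 0.809 SD |
| Power, assumed 0.3 SD | 31.8% | 18.0% |
| Power, assumed 0.5 SD | 69.7% | 41.0% |
| Power, assumed 0.8 SD | 97.7% | 79.1% |

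The plan's alternative test, Mann-Whitney U, was simulated with normal data, asymptotic p-values and 20,000 trials per point. Power at 0.5 SD was 68.3% with 50 per group and 38.3% with 25. Power reached about 80% at 0.58 SD and 0.84 SD respectively.

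**4. Effect on accrual**

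- 50 patients in 12-18 months: 50/18 = 2.8 to 50/12 = 4.2 per month.
- 100 patients, if the same window is assumed: 100/18 = 5.6 to 100/12 = 8.3 per month.
- 100 patients, if the Section 5.0 rate is assumed instead: 100/4.17 = 24 to 100/2.78 = 36 months.

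**The case against.** The contradiction itself is hard to dispute. The fair objections concern what is built on it.

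- **The SD figures rest on assumptions.** The protocol names no single primary endpoint, effect size or target power. Some stability outcomes, such as the IKDC ligament grades, are ordered categories to which a difference in SD does not directly apply. This stands. The figures illustrate scale for a continuous outcome and are not evidence of the defect.
- **The Mann-Whitney figures use normal data.** The plan would normally reach that test only after the Shapiro-Wilk check rejects normality, and with skewed scores power could be higher or lower. This also stands. The simulation shows only that the gap between the two sample sizes persists under the rank test.
- **The envelope count is inferred.** Section 5.0 does not say how many envelopes are prepared or how the list is balanced. One per patient with an even split is an assumption, though a natural one given that half the patients receive each implant.
- **The 2-year Study Duration does not discriminate.** Recruitment of 12-18 months plus the 2-year assessment puts the last patient's final visit at 12 + 24 = 36 to 18 + 24 = 42 months. If the entry means the whole study, it does not cover even the 50-patient plan. It therefore cannot be used to choose between the totals.
- **The accrual scenarios are conditional.** They show what would follow under each assumption. The protocol gives no basis for judging whether either total is feasible.

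None of these points removes the conflict between the Synopsis and Section 5.0, and the main correction does not depend on them.

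**Conclusion.** The concern holds. Two current sections give sample sizes that differ by a factor of 2 (100 versus 50 in total, 50 versus 25 per group), and nothing in the protocol shows which is intended. This is a wrong figure in a quantity the trial relies on and must be corrected. That conclusion rests on the text alone.

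The statistical size of the gap, 0.57 versus 0.81 SD detectable at 80% power, holds for a continuous outcome compared by t test with complete follow-up. Losses to follow-up would make both values larger.

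**What to change.** 1. State one total and one per-group number, identical in the Synopsis and Section 5.0. If the smaller is intended, change the Synopsis to 50 (25 per group). If the larger, change Section 5.0 to 100 (50 per group).
2. In Section 6.0, replace the unnumbered reference to the sample size with that number, and name the recruitment period.
3. Confirm whether the 12-18 month window applies to the chosen number.
4. Confirm that the envelope set matches the chosen total and split.

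Optionally, Section 6.0 could replace its assertion that the sample is large enough with the detectable difference for the chosen size (0.57 SD for 50 per group, 0.81 SD for 25). It would need to be labelled as assuming a t test on a named continuous outcome and complete follow-up. This goes beyond resolving the inconsistency.

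**Cost.** Wording only, if the chosen number is the one staff already work to. If 100 is intended and staff work to Section 5.0, 50 more patients must be recruited, through a faster rate or a longer window. If 50 is intended, the Synopsis target is halved. The protocol gives no expected accrual beyond 50 in 12-18 months, so the feasibility of the larger total would have to be established separately.

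### Patients are allocated in the operating room and could be masked at little cost, but section 5.0 does not say that they or the questionnaire staff are kept unaware of the implant

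*Combined protocol and SAP*

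**What the plan says.** Section 5.0 fixes the moment of allocation: "Patients will be randomized in the operating room through the opening of opaque, study-numbered envelopes prior to skin incision". The arms are the GMK Sphere (medial pivot, MP) and the GMK posterior stabilized (PS) prosthesis.

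Self-report is scheduled before surgery, immediately after it, at 6 weeks, at 3 and 6 months, and at "12 months post-operatively, and 2 years post-operatively". Section 5.0 lists as patient-reported the Oxford Knee Score, the Knee Society Score, VR-12, the Forgotten Joint Score (12 months only), the Kujala questionnaire (2 years only) and three PROMIS CATs. On how they are collected it says: "These questionnaires will be completed at the routine post-operative clinic visits or over the phone through PROMIS Assessment Center".

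Section 2.0 makes these scores part of the study goal, which is to "compare subjective and objective measures of knee stability following TKA with a medial pivot design compared with a posterior stabilized design".

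The document says nothing about who knows the implant after the envelope is opened. The words blind and mask do not appear in it.

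**The concern.** An opaque envelope opened just before incision protects against selection at entry. It does nothing for outcomes reported over the next two years by a patient who may know which design was implanted. Masking the examiners who grade stability would not help here either, because on these instruments the patient is the assessor.

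The subjective half of the objective rests on these scores. Item 10 of the Oxford score, for example, asks directly whether the knee feels as if it might give out. If knowing the design changes how patients answer, the resulting difference between arms cannot be told apart from an effect of the implant. The two-sample tests in section 6.0 cannot separate the two, and a larger sample only makes a biased difference more likely to reach significance.

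**Working it through.** **What the document provides after allocation**

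| Question | Where one would look | What is there |
|---|---|---|
| Is allocation concealed until surgery? | 5.0 | Yes: opaque, numbered envelopes opened in the operating room |
| Is the implant withheld from the patient afterwards? | 5.0, 6.0 | Not stated |
| Are clinic and phone questionnaire staff unaware of the arm? | 5.0, 7.0 | Not stated; 7.0 gives the investigators and authorized staff access to the records, with no separation of roles |
| Is the implant type restricted in the chart? | 5.0, chart review list | No; implant type is one of the items extracted |
| Does coding by study number mask treatment? | 5.0, risk paragraphs | No; it is offered against loss of privacy |

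Pre-operative scores precede allocation and are unaffected. The exposed assessments are the six post-operative time points.

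**Is there a source of expectation?** Section 1.0 describes MP as a newer design closer to normal kinematics and cites patients with one of each who "preferred their medial pivot knee to a PS, CR, or mobile-bearing (MB) design". It also cites a trial of 96 patients in which MP had lower range of motion, more complications and worse patient-reported outcomes than a mobile-bearing knee. Expectation is therefore plausible, but its direction is not settled.

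**Illustration of size.** The plan has no figure to reproduce: it gives no bias, SD, effect size or power. The inputs are:

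- Two-tailed t test at 0.05 (section 6.0).
- n per arm of 25 (section 5.0: 50 patients, half to each implant) or 50 (Synopsis: 100 patients, 50 per group). The two totals conflict, which is a separate point, so both are shown.
- b, the shift between arms in SD units caused by knowing the implant. This is an assumption, taken from 0 to 0.3.
- No true difference between the implants.

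The t statistic then follows a noncentral t distribution with df = 2n − 2 and noncentrality b × √(n/2). The rejection rate is P(T > t₀.₉₇₅) + P(T < −t₀.₉₇₅).

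- n = 25: df = 48, critical value 2.011, √(25/2) = 3.536.
- n = 50: df = 98, critical value 1.984, √(50/2) = 5.

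| b (SD) | Noncentrality, n = 25 | Rejection rate | Noncentrality, n = 50 | Rejection rate |
|---|---|---|---|---|
| 0 | 0 | 5.0% | 0 | 5.0% |
| 0.1 | 0.354 | 6.4% | 0.5 | 7.9% |
| 0.2 | 0.707 | 10.7% | 1.0 | 16.8% |
| 0.3 | 1.061 | 18.0% | 1.5 | 31.8% |

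The test is two-sided, so the rates are the same whichever arm the shift favours. Each rate applies to a single score with that shift. The shift need not be the same on a general-health form such as VR-12 as on a knee-specific score.

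**The case against.** The strongest objection is that silence does not show that patients are told. The consent pages are not in the supplied file, and a statement about disclosing the implant could well sit there. This stands: a reader might infer that the plan informs patients of their implant, and the document does not support that. What it supports is that section 5.0, which describes randomization and outcome collection in full, does not say whether patients or questionnaire staff are masked.

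Second, a reader might think masking would be free because allocation happens in the operating room. That also goes too far. The document does not say whether patients are awake when the envelope is opened, the implant type is in the medical record, and withholding it needs a consent statement and a rule on unmasking. The cost is small but not zero.

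Third, a reader might infer a bias in favour of MP from the background section. Section 1.0 cites evidence both ways and concludes that there is no consensus, and section 5.0 describes both prostheses as in common use. Nothing shows that patients receive the background text. If expectations differ between patients they may partly cancel, and the number who would learn their implant is unknown. This limits any claim about direction or size. It does not supply the missing protection.

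Finally, the IKDC grading and the KT1000 measurements are not self-report, so this point leaves that part of the objective largely untouched.

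**Conclusion.** The concern holds in a limited form. Late, concealed allocation makes patient masking feasible at little cost, and the supplied document does not provide for it. Post-operative self-reported outcomes up to 2 years are therefore not protected from expectation bias, and the planned analysis cannot remove such bias afterwards.

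The document fixes neither the size nor the direction. The rates of 6.4% to 18.0% (25 per arm) and 7.9% to 31.8% (50 per arm) rest on an assumed average shift of 0.1 to 0.3 SD with no true difference; with no shift the rate stays at 5%. They should not be read as the trial's actual false-positive rate.

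**What to change.** Add to section 5.0, and align the consent form, that:

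- subjects will not be told which prosthesis they received until their 2-year questionnaires are complete, unless disclosure is clinically necessary;
- staff who administer questionnaires, in clinic or by phone, will not have access to the allocation;
- once, after the 2-year questionnaires are completed, each subject will be asked whether they knew their implant and how they learned it, and any earlier unmasking will be recorded.

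The question should come after the questionnaires. Asked before the Forgotten Joint Score or Kujala, it would draw attention to the implant just before the scores it is meant to protect. Asked at 12 months, it might prompt patients to look the implant up.

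The cost is a short protocol and consent amendment and one question at an existing visit. The downside is that patients wait up to 2 years to learn their implant type, and some will learn it anyway from their records or because they were awake in the operating room.

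If masking is not feasible, section 5.0 should declare the trial open-label to patients, and the conclusions on patient-reported outcomes should be limited accordingly. If masking is already the practice or is already in the consent form, stating it in section 5.0 is enough.
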